Feasibility and acceptability. EASE has been piloted in a two-site, ongoing open clinical trial. Inclusion criteria included: 1) ages 12 to 17, inclusive; 2) a clinical diagnosis of ASD, confirmed by ADOS-2; 3) Verbal IQ score > 80; 4) Fluent in English; 5) Problems with ER per parent report; 6) Parent/guardian available to attend sessions. Exclusion criteria included: 1.) Serious suicidal/homicidal ideation; 2.) Past or current diagnosis of a psychotic disorder; 3.) Receiving concurrent psychotherapy treatment for emotional issues that overlaps with the current study.

Pilot data support the feasibility of recruitment (20 eligible participants enrolled within less than six months across two sites; there is now a rapidly growing waiting list for the larger trial), acceptability of EASE to consumers (based on quantitative and qualitative data and high retention rates), and viability of dissemination (high treatment fidelity across 8 therapists and 2 sites). Of the 20 participants who were eligible and enrolled in the program, two dropped out, 13 have completed the program (one of these is still completing post-treatment assessments) and 5 are ongoing with regular attendance; therefore data is available from 12 participants for preliminary analyses; of these, one had some missing pre-treatment data, and one had some missing post-treatment data, leaving 11 available for all measures except CGI. Table 1 summarizes the characteristics of the preliminary sample and the adolescent's satisfaction ratings provided at post-treatment.

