Preliminary efficacy evidence in adolescence. Pilot analyses indicate that EASE is associated with positive outcomes. Thus, far, Clinical Global Impressions-Improvement scores (made by an independent rater) that take functioning across environments and overall symptom impairment into account correspond to a mean of "Much Improved" (Mean = 2.25; SD = 0.63), with 100% of participants demonstrated at least some improvement, as determined by independently rated CGI-I. Table 1 shows the results of paired sample *t*-tests for participants who completed EASE by 9/25/17. Given the sample size available at the time, effect sizes provide better preliminary evidence of efficacy, with all but one achieving a Cohen's *d* effect size ( $d = |\text{Mean Difference}/\text{SD}|$ ) considered medium to large. Effect sizes on measures of ER were all medium-to-large, and functional improvement after treatment rated by an independent rater was quite large ( $d = 2.81$ ), signifying the potential benefits of ER intervention to adaptive function. Although the EDI scores did not reach significance ( $p = .06$ ), the effect size of EDI score was 0.74, notably higher than test-retest of EDI scores in a treatment stable sample ( $n = 432, d = -0.06$ ). Figure 1 illustrates the mean decreases in emotional reactivity, problem behaviors/irritability, and depression from baseline, to midpoint, to endpoint. Although these data are promising, they are not definitive given the small sample size and lack of a control group.

**Table 1.** Demographic information and self-report treatment satisfaction for participants who completed EASE

[figure not shown]
| n = 12   | M/SD, Range or %/n  |
|--|---|
| Age  | 14.7 (1.6)  |
| Race   | 75% (9) Caucasian, 16.7% Asian (2), 8.3% (1) African-American |
| Gender   | 81.3% male (n = 10)   |
| Full Scale IQ                                  | 102.8 (10.1); 83-115  |
| Baseline CGI-Severity                          | 4.43 (.67); 3 (mildly) to 5 (markedly) ill                    |
| How helpful was the program?*                  | 4.25 (.87)  |
| How much of an impact did the treatment have?* | 4.08 (.90)  |

\*On a 1 (not helpful/no impact) to 5 (very helpful/high impact) scale

**Table 2.** Preliminary Effect Size Estimates from Pre- to Post-EASE

[figure not shown]
| Construct                 | Measure                      | n | Mean Difference ( SD ) | d | t | p |

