**1.I.d. Sample and Ascertainment**

Sample. A sample of n = 80 male and female adolescents and young adults with ASD will be enrolled. The expected male to female ratio is 4:1, based on current prevalence estimates of diagnosed ASD. With a conservative estimate of 25% attrition, we would achieve a final sample size of 60. Pitt will enroll 50 participants, and VT will enroll 30 (due to budget restrictions and population access).

**Figure 6.** RCT Design

Inclusion criteria consist of: (1) an ASD diagnosis, based on expert clinical opinion and supported by ADOS-2; (2) age 14-21 years; (3) Verbal IQ  $\geq$  80; (4) fluency in English; (5) a parent available and willing to participate; (6) evidence of at least an average degree of ER impairment for ASD (T-score of 45 or higher or 0.5 SD below the mean; on the Emotion Dysregulation Inventory Reactivity Short Form); and (7) medications are permitted but must be stable for 4 weeks with no planned changes.

Exclusion criteria consist of: (1) Current suicidality or homicidality that warrants more immediate care; (2) active psychosis; (3) Receiving concurrent psychotherapy treatment for emotional issues (i.e., depression, anxiety, anger) that overlaps with the current study.

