## 1.J.a. STATISTICAL PLAN AND DATA ANALYSIS

### **Justification of sample size that is necessary to achieve the desired power**

We will enroll 80 subjects at two sites. Using small-scale pilot pre-post repeated measures data ( $n = 12$ ), we estimated the sample size to achieve the power of 0.80 for testing each hypothesis stated in the Aims 1 and 2 above from the EASE open trial. For the hypotheses to provide evidence that EASE has a differential treatment effect on ER, functional impairment, psychiatric symptoms, and problem behaviors (hypotheses 1a, 1b, 2a, 2b), Cohen's  $d$ , or standardized mean difference, ranged from small-to-medium effect size (0.41 for Anxiety) to very large (2.81 for CGI-I). The necessary sample size to detect the smallest effect size was computed as a total of 49 (per group), with a range of 4 to 28 per group for all other outcomes with larger effect sizes, and an average across measures of 17 per group. Our primary interest is in effects with at least moderate effect sizes, as they are likely to have the most real-world impact. As such, even if there was significant attrition, we should have ample power to detect the most meaningful outcomes for Aim 1 and Aim 2. To test the mediation effects (Exploratory Aim 4), we obtained the required sample size using the methodology proposed by Judd et al. (2001) and elaborated by Montoya & Hayes (2017). A necessary condition to detect mediation is that the change score for a mediator needs to be statistically significantly associated with the change score in dependent variable after controlling for the average level of the mediator. Using this framework, we found that the necessary total sample size to detect the mediation effect with power of .80 ranged from 43 to 86 (per group), where the effect size as a partial correlation in multiple linear regression ranged from large (0.44, path: Treatment  $\rightarrow$  CAMM Mindfulness  $\rightarrow$  RSQ Involuntary Disengagement) to medium (0.31, path: Treatment  $\rightarrow$  EDI reactivity  $\rightarrow$  Depression). The maximum sample size that we can feasibility ascertain for this project is 80, which gives us a chance to detect mediation processes that have large effects; accordingly, this aim is considered exploratory.

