**Intent to Treat Analyses and Approach to Missing Data.** Automated systems are in place via our online data collection (piloted during our open trial) to minimize occurrence of missing data. Nonetheless, intent-to-treat analyses of treatment effects will include all 80 individuals, regardless of attrition or infidelity to treatments. Both of our analytic approaches allow for missing data. ANOVA mixed models do not require that subjects be

excluded from the analyses because of a single missing data point. Multilevel growth models can also make an efficient estimation by utilizing all the available data, and further, the estimates are valid (i.e., asymptotically unbiased) when missingness occurs at random (MAR) (Little & Schenker, 1995). Even when MAR is not satisfied, the robustness of the results is maximized when all available data are used in the analysis (Schafer, 1997). In order to accommodate the case of missing ‘not at random,’ we plan to conduct a sensitivity analysis to see how much our inferences would be altered using a pattern-mixture model (Hedeker & Gibbons, 2006).

**Controlling Experimental-Wise Type I Error Rates.** The conduct of multiple tests of statistical inference can artificially increase Type I error rates. Several approaches will be used to control the experimental-wise error rate in this trial. First, analyses conducted to test the hypotheses of Aims 1 through 3 will be given priority over exploratory analyses conducted as part of Aim 4. Since these hypotheses about efficacy and durability of the proposed EASE program on ER and functional impairment have confirmatory nature from our prior studies and are the main hypotheses in this clinical trial, we will employ Hochberg’s correction (Hochberg, 1988) to control the experimental-wise error rate by adjusting p-values for multiple hypothesis tests in order to rigorously examine the treatment efficacy and durability. Second, in order to address the hypotheses in Aim 4, outcome measures will initially be aggregated into four multivariate composite domains (i.e., ER, functional impairment, psychiatric symptoms, and problem behaviors) based on internal consistency analyses and previous studies, which will reduce the number of hypothesis tests initially conducted. Then, exploratory analyses will be conducted for individual measures within these composite domains only if the overall multivariate composite demonstrates a significant mediation effect.

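### The claim of ample power under significant attrition rests on pilot completers' effects, makes no allowance for early stopping, and is not supported for a moderate effect

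*Combined protocol and SAP*

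**What the plan says.** Section 1.F (Feasibility and acceptability) gives the pilot's status: of 20 enrolled, "two dropped out, 13 have completed the program (one of these is still completing post-treatment assessments) and 5 are ongoing". Twelve participants had data for analysis, and 11 for every measure except the CGI. The paired tests that give the effect sizes are "for participants who completed EASE by 9/25/17".

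Section 1.J.a (sample size justification) takes these effects as its basis: "Using small-scale pilot pre-post repeated measures data", n = 12, and "we estimated the sample size to achieve the power of 0.80 for testing each hypothesis stated in the Aims 1 and 2 above". It says the main interest is in effects that are at least moderate, and concludes that "even if there was significant attrition, we should have ample power to detect the most meaningful outcomes for Aim 1 and Aim 2".

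Attrition is given a number only in section 1.I.d: "With a conservative estimate of 25% attrition, we would achieve a final sample size of 60".

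On who is analysed, 1.J.a gives two versions. Under Intent to Treat Analyses and Approach to Missing Data, "intent-to-treat analyses of treatment effects will include all 80 individuals, regardless of attrition or infidelity to treatments". Under General analytic approach, the intent-to-treat set is limited to participants with some exposure to their assigned treatment.

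**The concern.** The effects used for sizing describe people who finished EASE. The planned comparison also includes people who stop. If those who stop are measured afterwards and have gained less, the average EASE effect is smaller than the pilot d. The plan counts attrition only as lost numbers, so its statement about power under attrition does not cover this.

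At stake is how a null result would be read. A reader told that power was ample despite attrition could take it as evidence against EASE, when the trial may have had little better than an even chance, or less, of detecting a moderate effect.

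**Working it through.** **Inputs.** Pilot d values from the effect-size table in 1.F: CGI-I 2.81, RSQ 2.67, depression 0.88, ABC-I 0.79, EDI Reactivity 0.73 (0.74 in the text), anxiety 0.41. Power 0.80 (1.J.a). Equal allocation at each site (1.I.d), so 40 per arm. Attrition 25%: 80 × 0.75 = 60, or 30 per arm. Assumptions: two-sided alpha 0.05, which the sizing text does not state, and d = 0.50 for a moderate effect, which the plan does not quantify.

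**Step 1: the plan's own figure.** A one-sample (paired) t-test at two-sided 0.05 and power 0.80 gives:

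| Measure | d | n |
|---|---|---|
| CGI-I | 2.81 | 4 |
| RSQ | 2.67 | 4 |
| Depression | 0.88 | 13 |
| ABC-I | 0.79 | 15 |
| EDI | 0.73 | 17 |
| Anxiety | 0.41 | 49 |

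The mean is (4 + 4 + 13 + 15 + 17 + 49)/6 = 17. This reproduces the stated 49, the average of 17 and the lower bound of 4. The stated upper bound of 28 for the other outcomes does not follow from the tabulated effects. The match shows that the completer effects entered undiluted.

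**Step 2: two-arm power.** For n per arm, a two-sample t-test has noncentrality d × √(n/2) and 2(n − 1) degrees of freedom. If 25% of EASE participants stop and lose a share L of the benefit over control, with unchanged SD and outcomes still measured, the effect becomes d × (1 − 0.25 × L). The multiplier is 0.875 for L = 0.5 and 0.75 for L = 1.

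| Scenario | n per arm | Effect (EDI) | Noncentrality | Power | Effect (moderate) | Noncentrality | Power |
|---|---|---|---|---|---|---|---|
| No attrition | 40 | 0.73 | 3.26 | 0.897 | 0.50 | 2.24 | 0.598 |
| 25% lost, no dilution | 30 | 0.73 | 2.83 | 0.794 | 0.50 | 1.94 | 0.478 |
| All 80, leavers keep half | 40 | 0.639 | 2.86 | 0.805 | 0.4375 | 1.96 | 0.489 |
| All 80, leavers gain nothing | 40 | 0.5475 | 2.45 | 0.677 | 0.375 | 1.68 | 0.381 |

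**Step 3: when dilution is worse than lost numbers.** Setting power at 40 per arm with effect d × (1 − 0.25 × L) equal to power at 30 per arm with d gives L of about 0.55 for both effects. Below that loss of benefit, counting attrition as lost numbers is the more cautious choice.

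**Step 4: where the moderate-effect shortfall comes from.** Against 0.80, the gap with no attrition is 0.80 − 0.598 = 0.202. It is 0.322 with 30 per arm undiluted, 0.311 with half loss and 0.419 with full loss. So 0.202/0.311, about 65%, of the half-loss gap and 0.202/0.419, about 48%, of the full-loss gap are there before anyone leaves.

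**Step 5: the plan's paired formula.** EDI with full 25% dilution (0.5475) needs 29 per group, within 30. An undiluted d = 0.50 needs 34, more than 30.

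**Sensitivity figure.** Adding the two pilot dropouts as zero change to the EDI data (n = 11, mean 0.49, SD 0.67) gives mean 11 × 0.49/13 = 0.415, SD 0.639 and d = 0.65. Two-arm power at 40 per arm is then 0.82.

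**The case against.** The strongest reply is that attrition as lost numbers is not a lenient treatment. Half loss of benefit gives slightly more power (0.805) than 30 per arm (0.794), and dilution is worse only beyond about 55% loss. This stands.

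Dilution also needs outcome data after stopping, and no section promises to collect them. Section 1.J.a plans mixed and growth models on available data under missing at random, with a pattern-mixture sensitivity analysis. Those models do not enter leavers as zero change. If leavers give no further data, power lies near the 30-per-arm figure. This stands too, and it makes the dilution scenarios assumptions rather than predictions. It does not rescue the claim for a moderate effect, where the 30-per-arm figure is 0.478.

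On the plan's own paired formula, the EDI requirement survives full dilution (29 against 30). That is correct, but the formula describes one group before and after treatment, whereas the trial compares two arms. Whether a pre-post d can stand for a between-arm difference is a larger and separate question.

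A reader might go further and infer that the pilot contradicts the word conservative for the 25%. The documents do not support that. Two of 20 enrolled dropped out (10%), or 2 of the 15 whose course had ended (13%). Missing questionnaire data in completers are not attrition, and 1.F attributes some pilot missing data to early system faults. A reader might also infer a subtraction error in the 11 participants available for most measures. That is not established: the two reports of partly missing data may concern one person, or different measures.

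**Conclusion.** The point holds as a mismatch between the basis for sizing and the planned analysis, and as an unsupported statement about power. The effects come from completers, nothing discounts them for early stopping, and participants who attend only in part remain in the analysis under either stated analysis set.

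For the EDI at the pilot effect, power under 25% attrition ranges from 0.677 to 0.805, depending on what leavers lose and whether they are measured. Only the no-benefit case falls well below 0.80. It would be too strong to conclude that dilution by itself undoes the trial's power for the EDI. For d = 0.50, power is at most 0.598 and falls to between 0.381 and 0.489 under attrition, so ample is the wrong word for the effects the plan says it cares about most.

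The figures assume two-sided 0.05, pilot d values at face value, d = 0.50 as moderate, unchanged SD, and no adjustment for covariates or repeated measures. The planned Hochberg adjustment would lower them further.

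**What to change.** In the sample size justification of 1.J.a:

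- Replace the sentence on ample power with two-arm power at 30 per arm undiluted, and at 40 per arm with the effect multiplied by (1 − 0.25 × share of benefit lost) for losses of 50% and 100%. Give both for the EDI effect and for a stated moderate effect.
- Say that the pilot effects come from participants who completed EASE.
- Label the dilution as an assumption, and note that under missing at random with no data after dropout, power lies near the 30-per-arm figure.
- If the zero-change recalculation (EDI 0.73 to 0.65) is shown, present it only as a sensitivity figure, because no outcomes are reported for the two dropouts.

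Also in 1.J.a, reconcile the two definitions of the intent-to-treat set. The 25% in 1.I.d can stay as worded.

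The cost is a short calculation and some rewording. The sample size does not change, since the plan already treats 80 as the feasible maximum. The downside is a less favourable power statement.

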## 1.G. Need for Current Study and Impact

ER impairment, psychiatric symptoms, and problem behaviors exacerbate social deficits, increase distress, and interfere with the achievement of positive adult outcomes. Given that (1) outcomes tend to be poor in early adulthood for people without intellectual impairment, (2) psychiatric comorbidity is high, and (3) current psychosocial interventions are extremely limited in scope, and there is a need for an intervention that is appropriate for both adolescents and young adults with ASD that is mechanistically based. Although psychosocial interventions for ASD have burgeoned in recent years, there has been very little research aimed at remediation of the core therapeutic mechanisms of action (Lerner et al., 2012). Given evidence from multiple levels of analysis that many behavioral problems and psychiatric comorbidities in people with ASD arise from ER impairment, we have developed a psychosocial treatment specifically *targeting ER impairment via mindfulness* as the therapeutic mechanism of action. Based on our own prior research, including a two-site open trial of the program, and research by other teams, there is growing evidence that mindfulness can be targeted in ASD and that it leads to improved ability to manage intense emotion.

Potential impact of this research is substantial. EASE has the potential to impact a number of conditions that frequently co-occur with ASD, such as depression, reactive aggression/problem behavior, and anxiety. Given that the program was designed to be appropriate for adolescents and young adults, it takes a lifespan approach to promoting success during this critical, high-risk transition period. Finally, the program was developed using a participatory action approach, integrating perspectives from multiple stakeholders. This will ensure the final curriculum is maximally portable and easily disseminated once we demonstrate efficacy.

## 1H. AIMS

**The primary objective of this study is to formally evaluate efficacy of EASE via a sufficiently powered, two-site randomized-controlled trial (RCT).** Our aims are consistent with several FY17 ARP **areas of interest**; specifically, EASE: (1) is a behavioral, non-pharmacological therapy that (2) alleviates co-occurring conditions (e.g., depression, aggression, anxiety), and (3) promotes success during the transition to adulthood. This proposal is innovative in many aspects, perhaps most substantially in that it targets a theoretically and empirically based transdiagnostic process (i.e., impaired ER) during a critical transitional period during development. As such, and consistent with the spirit of the ARP Clinical Trial Award, this research is expected to have a major impact on the treatment of ASD.

A total of **80 adolescents and young adults with ASD** (age 14-21, inclusive) will be randomly assigned to either EASE or an active control condition (ACC), consisting of supportive therapy that is matched on therapist time to EASE but does not contain EASE's active ingredients (e.g., mindfulness).

### **Aim 1 (Primary Outcome): Show that EASE improves emotion regulation.**

- ❑ H1a: Participants in the EASE group will demonstrate a steeper decline in ER impairment, relative to the ACC group.
- ❑ H1b: Participants in the EASE group will demonstrate less reliance on maladaptive ER strategies, relative to the ACC group.

### **Aim 2 (Secondary Outcomes): Demonstrate that EASE results in decreased functional impairment and reduced psychiatric symptoms and problem behaviors.**

- ❑ H2a: Participants in the EASE group will demonstrate significantly decreased functional impairment after treatment, relative to the ACC group.
- ❑ H2b: Following treatment, participants in the EASE group will show significantly greater reductions in psychiatric symptoms and problem behaviors relative to the ACC group, including depression, aggression/problem behavior, and anxiety.

### **Aim 3 (Durability): Examine the trajectory of change including the degree to which effects are sustained after treatment completion.**

- ❑ H3a: Participants in the EASE group will maintain significantly greater gains in ER ability, functioning, and reduced psychiatric symptoms, and at 3-months post-treatment follow-up compared to ACC group.

- ❑ H3b: ER impairment will not return to pre-treatment levels three months after treatment completion.

[figure not shown]
#### Aim 4 (Exploratory - Mediators): Evaluate whether changes in ER and mindfulness mediate improvements.

- ❑ H4a: Decreased ER impairment will predict decreased functional impairment and psychiatric symptoms.
- ❑ H4b: Increased mindfulness will predict decreased ER impairment.

## II. Methodology

### 1.I.a. Experimental Intervention - EASE

Theoretical and mechanistic basis. EASE was designed to address the common ER profile in ASD, characterized by a tendency to react intensely without awareness or forethought (see [name] & [name], 2014a). High negative emotion and arousal, combined with poor emotional insight and self-monitoring, may result in fast emotion escalation and prevent the person from employing a healthy regulatory strategy. EASE addresses these obstacles by developing awareness of emotion at varying degrees of intensity, teaching strategies to regulate in the face of intense emotion, and practicing these skills in natural settings and applied to situations that elicit the most dysregulation for the client. In the EASE program, we provide a model for grouping strategies (see Figure 5: ABCD model), with the goal of helping the client learn that more than one strategy can be chosen, once the response is noticed in the moment (awareness). The four modules build upon one another: Awareness (building awareness of emotions and reactions), Breathe (intentionally focusing on mindful breathing before responding or judging), Change (reframing the thought or situation, or distancing self and emotion from the thought/situation), and Distract (temporarily re-focus attention to gain control).

**Figure 5.** ABCD Model of EASE

**Mindfulness is the cornerstone of EASE.** It is used to improve emotion awareness and encourage decentering of body- mind (separating the links between thoughts, feelings, and self), which is taught with focused meditative practices on present-moment experiences, thoughts, emotions, and body sensations (Baer, 2000; Kabat-Zinn et al., 1985). Improving awareness of internal reactions has consistently shown to target cognitive and emotional reactivity and mediate functional improvements in clinical and nonclinical populations (Gu et al., 2015). Finally, given that ER impairment often manifests in social situations, EASE’s treatment targets are addressed within the context of the individual’s unique personal social challenges and triggers. Prior to every session the therapist identifies a social ‘challenge’ relevant for the client. Although the curriculum provides suggestions for how to practice new ER skills during the social challenges, therapists use discretion and clinical judgment to personalize this component based on the client’s *Needs Assessment* (conducted online prior to the first session, by the youth and parent, separately).

Format. The EASE program includes sixteen 50 to 60-minute sessions over 16 weeks. The treatment is delivered individually by a therapist and is supported by parent involvement and online content. Each session begins with a mindful check-in, review of prior material, and agenda setting, then proceeds to skill teaching and practice, practice of a mindfulness exercise, and planning for post-session practice. EASE includes community sessions, which often occur outside of the clinic, in situations that are both challenging and relevant to the client’s daily life. This provides an opportunity to practice skills in a more natural environment, reinforce learning, and improve generalization. Both the client and parent also have access to emotionCoach (i.e., “eCoach”), the online platform for EASE that includes all of the intervention materials, audio recordings of mindfulness exercises, and additional tips and information. Having materials from session and information to

support the concepts introduced in session available online allows clients to learn and process information at their own pace and aids in synchronous learning for parents.

Use of **an individual therapy approach** permits flexibility in the delivery of the treatment and promotes dissemination in clinical settings where groups may not be practical. Based upon our pilot study, participants differed greatly in their presentation of impaired ER, likely ER triggers, and response to specific mindfulness strategies. An individual therapy modality allows the clinician to devote time to mindfulness practices that are especially challenging for the participant, and base other activities around the participant’s specific difficulties. We also found that the community sessions were instrumental in generalizing new skills, and these sessions would be limited logistically with a group modality. The goal of the community sessions in EASE is not to simply practice ER in social situations (as one might be able to achieve in a group format), but rather to apply the newly learned ER skills in settings and situations that most closely mimic the specific context where the participant experiences the most dysregulation. Further, the individual therapy format facilitates personalization to accommodate the person’s circumstances, which vary significantly in this age range (e.g., in school or working, living with parents or alone). Finally, we considered a predominantly individual therapy approach, supplemented by some group sessions. However, Co-I [name] has prior experience with this structure, experiencing numerous logistical barriers; further, such a structure would be a difficult model to translate into clinical practice.

[figure not shown]
